4.5.2 Data Collection and Follow-Up for Withdrawn Subjects

According to FDA regulations, when a subject withdraws from the study, the data collected on the subject to the point of withdrawal remains part of the study database and may not be removed.

A subject who discontinues study treatment needs to state whether he/she wishes to continue participating in the study and allow further data collection as part of long term follow-up. Subjects who choose to continue with the study will participate in follow-up visits and evaluations according to the protocol. Subjects who refuse to participate in follow-up will be withdrawn from the study.

Study data collected prior to a subject's withdrawal from the study will be included in the study analysis.

5.0 Study Drug

5.1 Description

Alisertib is supplied as the ECT dosage form in 10 mg strength, with dose strength expressed as the milligrams of active drug (free acid).

5.2 Treatment Regimen

Alisertib will be administered by mouth, twice daily on days of radiation treatment during the course of FSRT. All patients will receive 10 days of Alisertib, concurrent with 10 daily radiation treatments. The first dose should be administered on the day of, but prior to, the first radiation treatment. The dose of Alisertib will be determined according to the protocol.

During the maintenance therapy period, Alisertib will be administered by mouth, at 50 mg twice daily from day 1 to day 7 of a 21-day cycle. All patients will receive up to 18 cycles, or until tumor progression

5.3 Risks

Most Common ($\geq 30\%$)

- Nausea, diarrhea
- Decreased number of white blood cells, which may increase risk of infection
- Damaged mucous membranes in the mouth (mouth blisters)
- Decreased number of red blood cells (or anemia) which may cause feelings of tiredness
- Weakness or feeling tired
- Hair loss

Very Common (10% and $<30\%$)

- Pain, including muscle pain, chest pain, and pain from cancer
- Fever with or without decreased white blood cells
- Sleepiness or feeling drowsy
- Bleeding events with or without decreased number of blood platelets
- Cough
- Shortness of breath
- Rash/skin eruption
- Constipation
- Vomiting
- Decrease in weight or loss of appetite
- Fluid retention and swelling (e.g., hands, feet, legs)
- Headache
- Dehydration (decreased body fluids)
- Dizziness

Common ($>1\%$ and $<10\%$)

- Confusion and mental status changes
- Imbalance which can lead to falling
- Anxiety or depression
- Difficulty sleeping

- High or low blood pressure
- Itchy or dry skin
- Bruises
- Inflamed or dry eyes, blurred vision
- Dry mouth
- Difficulty or painful when swallowing, altered taste
- Upset stomach, flatulence
- Difficult or blocked bowel movements
- Hemorrhoids
- Runny nose, sinus or voice problems
- Numbness or tingling in hands or feet
- Abnormal heart rhythm
- Ringing in the ears
- Muscle spasms/weakness
- Fluid around the lungs or abdomen
- Increased sweating or chills
- Abnormal kidney function
- Abnormal liver function test
- Abnormal levels of blood sugar, chemistry, protein or blood clotting time
- Bacterial, fungal or viral infection
- Increased blood bilirubin
- Blood clot (usually in the legs)
- Loss of bladder control

Uncommon (< 1%)

Serious and treatment-related adverse events include: rhabdomyolysis (muscle breakdown that can damage kidneys), bone fracture, blistering skin reaction, multiple organ failure, deafness, shock, hepatic veno-occlusive disease (also known as sinusoidal obstruction syndrome), heart problems, agitation or irritability, and injury to one or more organs that may be life-threatening or fatal.

5.4 Method of Assigning Subjects to Treatment Groups

This is an open label phase I study.

5.5 Preparation and Administration of Study Drug

Alisertib will be administered on an empty stomach with the patient remaining NPO (nothing by mouth), except for water and prescribed medications, for 2 hours before and 1 hour after each dose. Patients will be instructed to take each oral dose of Alisertib with 8 ounces (1 cup, 240 mL) of water.

Alisertib will be supplied as 10 mg ECT, with the dose strength expressed as milligrams of active drug (free acid). All tablets are to be ingested whole; patients who have difficulty swallowing tablets will be excluded from the study.

5.6 Subject Compliance Monitoring

Records of study medication used, dosages administered, and intervals between visits will be recorded during the study. The radiation treatment record will be reviewed and recorded.

5.7 Prior and Concomitant Therapy

Anti-emetogenic agents may be administered at the discretion of the investigator. Although not prohibited, the use of benzodiazepines for the prophylaxis or treatment of nausea or vomiting is discouraged because of the potential benzodiazepine-like effects of Alisertib.

Other medications, such as PPIs, H2 antagonists, growth factors, glucocorticoids, anti-emetics, and anti-epileptics are permitted at the treating physician's discretion.

All patients will receive concurrent FSRT to the recurrent glioma.

5.8 Packaging

Alisertib will be supplied as 10 mg ECT, with the dose strength expressed as milligrams of active drug (free acid).

5.9 Blinding of Study Drug

5.10 Receiving, Storage, Dispensing, and Return

5.10.1 Receipt of Drug Supplies

Millennium will provide Alisertib.

Upon receipt of the study treatment supplies, an inventory must be performed and a drug receipt log filled out and signed by the person accepting the shipment. It is important that the designated study staff counts and verifies that the shipment contains all the items noted in the shipment inventory. Any damaged or unusable study drug in a given shipment (active drug or comparator) will be documented in the study files. The investigator must notify study sponsor of any damaged or unusable study treatments that were supplied to the investigator's site.

5.10.2 Storage

Alisertib must be stored in a secure area according to local regulations.

The investigator must ensure that it is stored in accordance with the environmental conditions as determined by Millennium and defined in the Investigator Brochure or SmPC/reference label. Alisertib must be stored at room temperature.

5.10.3 Dispensing of Study Drug

It is the responsibility of the investigator to ensure that Alisertib is only dispensed to study subjects. The Alisertib must be dispensed only from official study site by authorized personnel according to local regulations.

5.10.4 Return or Destruction of Study Drug

It is the responsibility of the investigator to ensure that a current record of Alisertib disposition is maintained at each study site where Alisertib is inventoried and disposed of. Records or logs

must comply with applicable regulations and guidelines and should include:

- Amount received and placed in storage area.
- Amount currently in storage area.
- Label ID number or batch number and use date or expiry date.
- Non-study disposition (e.g., lost, wasted, broken).

At the completion of the study, there will be a final reconciliation of drug shipped, drug consumed, and drug remaining. This reconciliation will be logged on the drug reconciliation form, signed and dated. Any discrepancies noted will be investigated, resolved, and documented prior to return or destruction of unused study drug. Drug destroyed on site will be documented in the study files.

6.0 STUDY PROCEDURES

6.1 Study Visit Schedule

Please see *Appendix II* for study calendar.

6.2 Definition of Dose-Limiting Toxicities

Dose-limiting toxicities (DLTs) will be graded in severity according to the guidelines outlined in the NCI-CTCAE version 4.0. Dose-limiting hematologic and non-hematologic toxicities will be defined differently, and will be based on events that occur during study drug administration and for 30 days after the completion of the radiation therapy. In order to be declared a dose-limiting toxicity, an adverse experience must be related (definitely, probably, or possibly) to study therapy.

If a patient experiences a DLT during the radiation phase or the 30 day post radiation observation period, the patient will be permanently discontinued from study.

A dose-limiting toxicity (DLT) will be defined as follows:

- All grade 3 or higher toxicities that occur during or within 30 days of completing radiation treatment will be considered “treatment related” with the exception of (1) symptoms that are clearly related to the cancer or other pathology (in the opinion of the treating physician), and (2) expected sequelae of the neurosurgical procedure or radiosurgery. All neurological symptoms will be considered “treatment related” unless they are present at study onset, expected sequelae of the neurosurgical procedure, or clearly related to disease progression.
- Febrile neutropenia (even in the absence of hospitalization)
- Hematologic DLTs will be defined as either Grade 4 neutropenia lasting for ≥ 7 days in duration, any Grade 4 anemia, any Grade 4 thrombocytopenia, or any Grade 5 hematologic toxicity. All patients will be evaluated for hematologic toxicity.
- Any neurological toxicity of Grade 3, 4 or 5 will be considered a DLT, with the exception of 1) symptoms present prior to study enrollment, and 2) expected sequelae of the neurosurgical procedure.
- Grade 3 event of hypocalcemia, hypophosphatemia, hypokalemia, or hypomagnesemia lasting more than 24 hours without responding to medical therapy; or responding to medical therapy and lasting more than 72 hours
- Grade 3 transaminases elevation associated with \geq grade 2 bilirubin elevation (Hy’s law)

will also be a DLT defining event.

- Non-hematologic dose-limiting toxicity will be defined as any Grade 3, 4 or 5 non-hematologic toxicity, with the specific exception of:
 - Grade 3 nausea or Grade 3 vomiting that in the opinion of the Investigator occurs in the setting of inadequate compliance with supportive care measures and lasts for less than 48 hours.
 - Grade 3 diarrhea that in the opinion of the Investigator occurs in the setting of inadequate compliance with supportive care measures and lasts for less than 48 hours.
 - Grade 3 dehydration that, in the opinion of the Investigator occurs in the setting of inadequate compliance with supportive care measures and lasts for less than 48 hours.
 - Grade 3 acidosis or alkalosis which responds to medical intervention by returning to \leq Grade 2 within 48 hours.
 - Isolated Grade 3 elevation of liver function tests (LFTs) without associated clinical symptoms, lasting for \leq 14 days in duration.
 - Grade 3 hypocalcemia, hypokalemia, hypomagnesemia, hyponatremia, or hypophosphatemia which responds to medical intervention.
 - Grade 3 hypercholesterolemia.
 - Grade 3 hypertriglyceridemia.
 - Grade 3 alopecia

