6.4 Dose Delay and Dose Modification

If a patient experiences DLT during the radiation phase or 30 day post radiation observation period the patient will be permanently discontinued from the study.

Maintenance treatment with Alisertib will be repeated every 21 days. In order for a new cycle of therapy to begin, the patient's ANC must be $\geq 1,500/\text{mm}^3$ and the platelet count must be $\geq 75,000/\text{mm}^3$. In addition, any other toxicity considered by the investigator to be related to therapy with Alisertib must have resolved to \leq Grade 1 or to the patient's baseline value before a new cycle of therapy may begin.

If the patient fails to meet the above-cited criteria for retreatment, then initiation of the next cycle of therapy will be delayed for up to 1 week. At the end of that week, the patient will be re-evaluated to determine whether the criteria for retreatment have been met. Should treatment need to be delayed for more than 1 week (i.e., a rest period of more than 21 days) because of incomplete recovery from treatment-related toxicity, the dose of Alisertib will be reduced 1 level when therapy resumes. A second dose reduction may occur should treatment need to be delayed for more than 1 week because of incomplete recovery from treatment-related toxicity on the reduced dosage. Should treatment need to be delayed for more than 2 weeks at any dose, therapy with Alisertib will be discontinued (Table 1).

Dose Level	Dose	Schedule
1	50 mg	PO BID
-1	40 mg	PO BID
-2	30 mg	PO BID
-3	Discontinue	
Level 1 is the standard maintenance dose of 50 mg BID.		

Dose Modifications for Hematological Toxicity

If a patient experiences any of the following hematological toxicities during the dosing period, dosing will be discontinued for the remainder of that cycle and the dose will be decreased 1 level for all subsequent cycles of treatment.

1. _____
2. Grade 4 thrombocytopenia (platelet count $< 25,000/\mu\text{L}$) lasting more than 7 consecutive

days

3. Grade 3 neutropenia with fever or infection, or both, where fever is defined as an oral temperature greater than 38.5°C
4. Grade 3 thrombocytopenia with clinically significant bleeding

If a patient has a platelet count of less than 10,000/ μ l at any time, the patient will be removed from the study permanently.

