Appendix II: Visit Schedule

	Prior to Registration	Pre-treatment	Concurrent phase		Observation phase	Maintenance phase	Recommended Follow up
Time (day)	-14 to -1	-30 to -1	1-7	8-14	Day 13-42	From Day 43 to 1 year	Year 2 and onwards
Informed consent	X						
Demographics	X						
Medical history	X	X					
H & P	X	X	X ⁷	X ⁷	X ⁵	Q 2 months	X ⁶
Neuro exam	X	X	X ⁸	X ⁷	X ⁵	Q 2 months	X ⁶
MMSE		X			X ⁵	Q 2 months	X ⁶
QoL		X			X ⁵	Q 2 months	X ⁶
Vitals		X	X ⁷	X ⁷	X ⁵	Q 2 months	X ⁶
Weight		X	X ⁷	X ⁷	X ⁵	Q 2 months	X ⁶
KP/ECOG	X	X	X	X ⁷	X ⁵	Q 2 months	X ⁶
CBC w diff	X	X	X ⁷	X ⁷	X ⁵	Weekly ³	X ⁶
CMP, Mg +	X	X	X ⁸	X ⁷	X ⁵	Q 2 months	X ⁶
PT/PTT/INR		X					
Lipid Panel			X ⁷	X ⁷	X ⁵	Q 2 months	
EKG		X					
b-HCG	X ⁹						
MRI Brain		X			X ¹	Q 2 months	X ⁶
Treatment:							
RT			X ²	X ²			
MLN8237			X ³	X ³		X ⁴	

Q = every

H & P = History & Physical

NOTE:

1. Brain MRI should be done between days 35-42, then every 2 months for 1st year.
2. RT: daily on weekdays for a total of 10 treatments.
3. Alisertib: BID on days of RT only.
4. Alisertib: 50 mg BID on days 1-7 every 21 days, for up to 18 cycles or until progression.
5. Between day 39 to day 45 (at the end of 30 day observation period), then every 2 months
6. Every 3 months from year 1 to year 2, then every 4-6 months afterwards.
7. All items only need to be done at least once during week 1 and at least once during week 2.
8. Until discontinuation of Alisertib.
9. Pregnancy test should be done within 7 days prior to registration, if applicable

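### Sections 6.2 and 6.4 take a patient with a DLT off the study, section 4.5.2 keeps willing patients in follow-up after treatment stops, and no rule says how PFS, OS and QoL are handled after a DLT

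*Combined protocol and SAP*

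**What the plan says.** Section 6.2: if a DLT occurs in the radiation phase or the 30 days of observation after it, "the patient will be permanently discontinued from study". Section 6.4 opens with the same rule: "the patient will be permanently discontinued from the study". Later in 6.4, for a platelet count below 10,000/µl at any time, "the patient will be removed from the study permanently". Where 6.4 means only a treatment stop, it speaks of discontinuing Alisertib therapy.

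Section 4.5.2 takes another route. A subject who stops study treatment "needs to state whether he/she wishes to continue participating in the study and allow further data collection as part of long term follow-up". Then: "Subjects who choose to continue with the study will participate in follow-up visits and evaluations according to the protocol". And: "Subjects who refuse to participate in follow-up will be withdrawn from the study". Data collected before withdrawal stay in the analysis.

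Section 4.5.1 asks for End of Study procedures at withdrawal. Appendix II has no End of Study column. It places the first post-baseline brain MRI on days 35-42 and, by note 5, the first post-baseline QoL form as follows: "Between day 39 to day 45 (at the end of 30 day observation period), then every 2 months".

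Section 7.2 measures PFS and OS from the first day of radiation and gives no censoring rule. Section 7.3 analyses all subjects who had protocol radiation and concurrent Alisertib, for primary and secondary analyses.

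**The concern.** Whether a patient is still followed at 6 months should not depend on toxicity, and under the literal text of 6.2 and 6.4 it does. The secondary objectives are 6-month PFS, time to progression, OS and impact on QoL. A patient removed at a DLT supplies no later MRI, questionnaire or survival date. Kaplan-Meier would then treat that patient as having the same future risk as those who tolerated treatment, which is an assumption the trial could not check.

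QoL is the most exposed. No form is scheduled during the concurrent phase, so a patient whose DLT falls before the day 35-42 MRI and day 39-45 QoL windows may have no post-baseline assessment beyond an exit visit whose content is not defined. Section 7.2 says that the MTD-cohort estimates will help size a phase II trial, and that cohort is only 6-8 patients, so one patient lost is a noticeable fraction.

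**Working it through.** **1. The plan's own figures.** At a true DLT rate of 50%:
- escalate after 3: 0.5³ = 0.125;
- stop at 3 (2 or 3 DLTs): 0.375 + 0.125 = 0.500;
- escalate over both stages: 0.125 + 0.375 × 0.125 = 0.1719, or 17.2%.

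Four levels (20-50 mg BID) × 6 = 24 patients. All match section 7. None depends on what happens after a DLT, so the primary endpoint is not touched.

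**2. The passages side by side.** A DLT patient necessarily stops treatment, so 4.5.2 applies on its face: ask, follow if willing, withdraw only on refusal. Sections 6.2 and 6.4 apply to the same patient and withdraw without asking. No passage says which governs.

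**3. Timing.** Ten weekday fractions from a Monday start run from day 1 to day 12. Adding 30 days gives day 42, as in Appendix II (observation on days 13-42). A DLT before day 35 precedes both the MRI and the QoL windows. The documents give no distribution of DLT times, so the share of DLTs that early is unknown.

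**4. How many patients.** The decision rule itself allows at most 1 of 6 (17%) with a DLT at an acceptable dose, and requires at least 2 of 3-6 (33% or more) at a dose that stops escalation. For the whole trial the documents give no DLT rates, so they are assumed here. The section 6.3 rule was simulated (levels 1-4, 20,000 runs per curve). The last two columns are share × an assumed difference in 6-month PFS between DLT and other patients. This approximates the bias if DLT patients are censored before any event.

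| Assumed DLT rate, levels 1-4 (%) | DLT share of treated | Shift, 10-point difference | Shift, 20-point difference |
|---|---|---|---|
| 2/5/8/12 | 6.9% | 0.7 | 1.4 |
| 5/5/10/20 | 10.0% | 1.0 | 2.0 |
| 5/10/20/35 | 16.2% | 1.6 | 3.2 |
| 10/20/30/40 | 21.1% | 2.1 | 4.2 |

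Filling the top level to 6 gives 7%, 11%, 17% and 21%, or 1.2 to 3.0 DLT patients per trial. A steeper assumed curve (15/25/40/50%) gives 23.9% and 3.2 patients; 0.239 × 20 = 4.8 points. Hence roughly 1 to 5 points.

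**5. The MTD cohort.** Take six patients, one with a DLT and unscored, and 2 of the other 5 progression-free at 6 months. The scored estimate is 2/5 = 40%. If the unscored patient progressed, it is 2/6 = 33%; if not, 3/6 = 50%.

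**The case against.** The strongest reply is that the protocol uses the word study loosely. Section 4.5.1 lists progressive disease as a reason to withdraw a patient from the study although OS is an objective. Section 4.5.2 is headed as being about withdrawn subjects yet offers them follow-up. The off-study case report form has separate dates for last study agent, on and off follow-up, and off study. A site could reasonably read 6.2 as a treatment stop and continue follow-up. That stands as a possible reading, but the text does not establish it: 6.4 has different wording for a treatment stop, and nothing ranks 4.5.2 above 6.2.

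A reader might infer that outcomes for DLT patients cannot be scored and that the estimates rest on patients without a DLT. The documents do not support that. Section 7.3 has no DLT exclusion, data before withdrawal are kept, and a progression or death before removal counts. Early censoring is the likely result. A narrower gap does remain: 7.3 requires radiation according to the protocol, so a patient whose DLT cuts radiation short might fall outside the analysis set.

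Nor do the documents show that most DLTs come before the first MRI or QoL form. The platelet rule applies at any time and sits among the maintenance modifications, so it may act well after those assessments.

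On size, the reply is largely right. Section 7.2 plans response and median survival, not 6-month PFS, for the MTD cohort, and already calls the intervals very wide. The exact 95% interval for 2/6 is 4% to 78%, which dwarfs a shift of a few points.

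**Conclusion.** The point holds as a contradiction with an analysis consequence. Followed literally, 6.2 and 6.4 end PFS, time-to-progression, OS and QoL follow-up because of toxicity, while 4.5.2 would continue it for willing patients. No censoring rule fills the gap.

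The effect is modest and confined to descriptive secondary estimates: about 7-21% of treated patients on the four main assumed curves, and a shift of roughly 1-5 points in 6-month PFS across all the curves tried. Both figures rest on assumed DLT rates and an assumed 10-20 point outcome difference. In the MTD illustration the direction is not established, since the bounds of 33-50% lie on both sides of 40%. The wording should be corrected because the change is cheap and follow-up not collected at the time may not be recoverable. It does not threaten the MTD determination.

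**What to change.** Reconcile 6.2 and 6.4 with 4.5.2 by separating off treatment from off study, for both the DLT sentences and the platelet sentence. The rules on when treatment stops stay as they are. State that:

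- a patient who stops treatment for a DLT or under the platelet rule is offered continued follow-up under 4.5.2, with the patient's agreement, on the existing Appendix II schedule (MRI, QoL, survival);
- the patient is included in the PFS, OS and QoL analyses from the first day of radiation, including where a DLT shortened radiation;
- the patient is censored at last assessment (PFS) or last contact (OS) only if follow-up is refused or lost.

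Define in Appendix II what the End of Study visit collects, so that a patient who refuses further follow-up still has a known exit assessment.

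The cost is wording in a few sections and, compared with a literal reading of the present text, the scheduled visits for about 1-3 more patients. No additional enrolment or new type of assessment is needed.

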6.3 Dose escalation/de-escalation

Dose escalation will proceed within each cohort according to a “3+3 design”, as explained in the following scheme. Dose-limiting toxicity (DLT) is defined above. The toxicity assessment period is 30 days after the completion of the radiation therapy.

Dose Level	Alisertib dose
-1	10 mg BID
1	20 mg BID
2	30 mg BID
3	40 mg BID
4	50 mg BID (final dose level)

Number of Patients with DLT at a Given Dose Level[†]	Escalation Decision Rule
0 out of 3	Enter 3 patients at the next dose level.
≥ 2	Dose escalation will be stopped. This dose level will be declared the maximally administered dose (highest dose administered). Three (3) additional patients will be entered at the next lowest dose level if only 3 patients were treated previously at that dose.
1 out of 3	Enter at least 3 more patients at this dose level. 
 • If 0 of these 3 patients experience DLT, proceed to the next dose level.

	
 If 1 or more of this group suffer DLT, then dose escalation is stopped, and this dose is declared the maximally administered dose. Three (3) additional patients will be entered at the next lowest dose level if only 3 patients were treated previously at that dose.
≤1 out of 6 at highest dose level below the maximally administered dose	This is generally the recommended phase 2 dose. At least 6 patients must be entered at the recommended phase 2 dose.
†Dose escalation will be determined based on the occurrence of DLTs. For the purposes of determining whether to advance the Dose Level, DLTs will be counted by patient (i.e., a patient who experiences more than 1 DLT will be counted only once).	

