--	---

Study Therapy, Dose, Route, Regimen	Alisertib (MLN8237) will be administered by mouth, twice daily. The dose of Alisertib will be defined by the protocol.
Duration of administration and follow-up	Concurrent with radiation treatment, then 30 days after finishing radiation therapy will receive twice daily from day 1-7, every 21 day cycle for up to 18 cycles, or until tumor progression.
Reference therapy	None. This is a phase I study
Statistical Methodology	We will use a two-stage accrual design at each dose considered. We will initially enter 3 subjects at each dose. If none of the three experiences a dose-limiting toxicity we will proceed to the next dose. If one of the three experiences toxicity at that level, we will accrue 3 more subjects at that dose. If at any time there are two or more dose-limiting toxicities (in the 3-6 subjects) on a given dose, we will terminate accrual to the Phase I portion of that trial. No patient will be treated at a higher dose until the 3 or 6 patients have completed their toxicity evaluation period at the current dose. With this plan, a dose with a 50% or greater probability of causing a dose-limiting toxicity has at most a 12.5% chance of satisfying the conditions for dose escalation after the first 3 subjects and at least a 50% chance of stopping at 3. With the two-stages (3-6) together, there is at most a 17.2% chance of escalation.

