Schema	 
The flowchart illustrates the study schema. It begins with a box: "FSRT (35 Gy in 3.5 Gy fractions)+ MLN8237 20 mg BID on days of RT". This leads to a decision diamond "DLT?". If "Yes", it leads to "FSRT (35 Gy in 3.5 Gy fractions)+ MLN8237 10 mg BID on days of RT". If "No", it leads to "FSRT (35 Gy in 3.5 Gy fractions)+ MLN8237 30 mg BID on days of RT". This second step also leads to a "DLT?" diamond. If "Yes", it leads to "No further escalation". If "No", it leads to "FSRT (35 Gy in 3.5 Gy fractions)+ MLN8237 40 mg BID on days of RT". This third step leads to a "DLT?" diamond. If "Yes", it leads to "No further escalation". If "No", it leads to "FSRT (35 Gy in 3.5 Gy fractions)+ MLN8237 50 mg BID on days of RT", which is labeled as the "Final dose level". A large blue arrow labeled "30 days Since finishing FSRT (no treatment)" points from the final dose level box to a yellow box on the right labeled "Maintenance Treatment". The maintenance treatment box contains the text: "MLN8237 50 mg BID on days of RT every 21-day cycle up to 18 cycles, or until tumor progression".

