7.2 Statistical Methods

We will use a two-stage accrual design at each dose considered. We will initially enter 3 subjects at each dose. If none of the three experiences a dose-limiting toxicity we will proceed to the next dose. If one of the three experiences that level of toxicity, we will accrue 3 more subjects at that dose. If at any time there are two or more dose-limiting toxicities (in the 3-6 subjects) on a given dose, we will terminate accrual to the Phase I portion of that trial. No patient will be treated at a higher dose until the 3 or 6 patients have completed their toxicity evaluation period at the current dose. With this plan, a dose with a 50% or greater probability of causing a dose-limiting toxicity has at most a 12.5% chance of satisfying the conditions for dose escalation after the first 3 subjects and at least a 50% chance of stopping at 3. With the two-stages (3-6) together, there is at most a 17.2% chance of satisfying the conditions for dose escalation after the 6 subjects.

The maximally tolerated dose (MTD) will then be the last dose studied or the previous dose, based on Investigator's clinical judgment of the degree of toxicity seen at the last dose. While waiting for the 3 or 6 subjects accrued according to plan to complete their toxicity evaluation period, up to 3 additional subjects may be accrued at the current dose. These additional subjects will not count towards the formal plan of stopping at two or more toxicity occurrences, but will contribute to the judgment as to the MTD.

We will also conduct some descriptive analyses that will help in the design of a possible phase-II trial. Among patients at the MTD in each arm, we will estimate the proportion with complete or partial response, as well as the median survival (through the Kaplan-Meier method). We will also compute associated 95% confidence intervals, although we realize that they will be very wide (given that we only anticipate 6-8 patients to be treated at the MTD in each arm). The estimates themselves, however, will help in the sample size calculations of possible future phase-II trials.

Progression free survival and overall survival will be measured from the date of starting study treatment (first day of radiation treatment). Progression free survival will be assessed by the treating physician based on the brain MRI.

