8.4 Stopping Rules

Enrollment will stop if there are two or more DLTs in any one dose cohort and the MTD will be defined as the next lowest dose.

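### If 20 mg BID has two or more DLTs, the schema and 6.3 point to a 10 mg BID cohort, but 7.2 and 8.4 end accrual and 8.4 makes untreated 10 mg BID the MTD

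*Combined protocol and SAP*

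**What the plan says.** All of the following is current, operative text in the combined protocol and SAP.

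- **Schema (Study Summary).** A DLT at the 20 mg BID starting dose leads to "MLN8237 10 mg BID on days of RT". The decision box asks only whether a DLT occurred and gives no threshold.
- **6.3, dose table and rules.** 10 mg BID is listed as level -1, below level 1 at 20 mg BID. With two or more DLTs, "Dose escalation will be stopped". Both stopping rows then add: "Three (3) additional patients will be entered at the next lowest dose level if only 3 patients were treated previously at that dose". The last row asks for at least 6 patients, with at most 1 of 6 having a DLT, at the recommended phase 2 dose.
- **Study Summary, Statistical Methodology.** The row sets its limit at a second DLT and reads: "toxicities (in the 3-6 subjects) on a given dose, we will terminate accrual to the Phase I portion of that trial".
- **7.2.** It repeats the stop: "we will terminate accrual to the Phase I portion of that trial". It then says "The maximally tolerated dose (MTD) will then be the last dose studied or the previous dose", with the choice left to clinical judgment.
- **8.4.** The stop reads: "Enrollment will stop if there are two or more DLTs in any one dose cohort". For the dose to report, the same sentence says that "the MTD will be defined as the next lowest dose". No exception is made for the starting level.

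**The concern.** A level below the starting dose has one use: to be opened when the starting dose proves too toxic. In exactly that case the plan gives incompatible instructions. One set points to treating patients at 10 mg BID. The other closes enrollment and, in 8.4, attaches the MTD label to 10 mg BID anyway.

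The MTD is a primary objective (1.1.2, 2.1) and the primary safety endpoint (3.4). A team that follows 8.4 as written would report a primary result with no observation behind it, and would skip the cohort that could have supplied one. A team that follows the schema would be enrolling after a stopping rule had been met.

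**Working it through.** **1. The plan's own figures.** Section 7.2 gives operating characteristics at a DLT probability of p = 0.5:

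- Escalate after 3: (1-p)^3 = 0.5^3 = 0.125 (stated 12.5%).
- Stop at 3: 3p^2(1-p) + p^3 = 0.375 + 0.125 = 0.50 (stated 50%).
- Escalate over both stages: (1-p)^3 + 3p(1-p)^2 × (1-p)^3 = 0.125 + 0.375 × 0.125 = 0.1719 (stated 17.2%).

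All three reproduce. The fault lies in the rules, not in the arithmetic.

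**2. The rules side by side, after two or more DLTs at 20 mg BID.**

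| Source | Next patients | Dose named |
|---|---|---|
| Schema; 6.3 level -1 row | 10 mg BID, number not given | none yet |
| 6.3 step-down sentence | none: its condition is 3 already treated, and level -1 has 0 | none |
| 7.2 and Study Summary | none | 7.2: 20 mg BID, which just failed, or a previous dose that was never studied |
| 8.4 | none | MTD = 10 mg BID, with 0 treated |

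Section 6.3 halts escalation and still enrolls at a lower level, whereas 7.2 and 8.4 halt enrollment altogether. The same clash therefore affects a stop at levels 2 to 4: 6.3 asks for 3 more patients one level down, and 7.2 and 8.4 do not let them in. Level 1 is the worst case because the level below it has no patients at all.

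If level -1 were opened and also had two or more DLTs, 8.4 would name a dose that is not on the ladder.

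**3. Chance of reaching the branch.** The inputs are the 3+3 rules in 6.3 and 7.2, plus an assumed true DLT rate p at 20 mg BID, because the documents give none for the combination. Patients are taken as independent, and only formal-plan patients count.

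P(two or more DLTs in 3-6) = 1 - [(1-p)^3 + 3p(1-p)^5]

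| Assumed p | (1-p)^3 | 3p(1-p)^5 | P(branch) |
|---|---|---|---|
| 5% | 0.857 | 0.116 | 0.027 |
| 10% | 0.729 | 0.177 | 0.094 |
| 15% | 0.614 | 0.200 | 0.186 |
| 20% | 0.512 | 0.197 | 0.291 |
| 25% | 0.422 | 0.178 | 0.400 |
| 30% | 0.343 | 0.151 | 0.506 |

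**4. What a treated cohort adds.** With 0 patients, the DLT rate at the named MTD could be anything from 0% to 100%. The exact (Clopper-Pearson) two-sided 95% interval for 0/6 has upper limit 1 - 0.025^(1/6) = 0.459, giving 0% to 46%. For 1/6 it is 0.4% to 64%. Six patients give a wide interval, but it is an interval based on data.

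**The case against.** The strongest reply is that the intent is plain. Section 6.3 covers de-escalation by title and lists level -1, and the schema agrees. The step-down clause is a sensible way to complete a cohort at lower levels already visited, and it does not forbid opening level -1. Staff would probably treat patients at 10 mg BID, and the quarterly reports in 10.1 must say whether a stopping criterion was met, so the event would reach the DSMC. This stands as evidence of intent. It does not supply a cohort size for level -1, and it does not cancel 8.4, which those same reports would show as triggered.

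A second reply is that the 6-patient minimum in 6.3 prevents an untested dose from going forward. It does bar 10 mg BID as the recommended phase 2 dose. It does not remove the MTD label that 8.4 assigns, and the 8.4 stop prevents the minimum from being met.

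Stronger readings are tempting but not supported:

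- A reader might infer that the branch is unlikely because FSRT alone produced no grade 3 or higher toxicity in 20 patients (1.2.2; exact 95% upper limit 1 - 0.025^(1/20) = 17%). That series was without alisertib, so its upper limit cannot bound the DLT rate of the combination. In addition, 6.2 presumes most grade 3 or higher events to be treatment related. Only the table of assumed rates stands.
- A reader might take the table as the chance of a wrong MTD. It is the chance of meeting contradictory instructions; what follows depends on which one is obeyed.
- A reader might infer that a single DLT at 20 mg BID triggers de-escalation, since the schema shows no threshold. The threshold of two or more comes from 6.3, 7.2 and 8.4.
- A reader might see a safety hazard. The literal stop exposes no further patient.

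**Conclusion.** The point holds as an internal contradiction that yields an unsupported primary result on one branch. Obeyed literally after level 1 fails, 8.4 declares an MTD at a dose that no patient received, and 7.2 offers either the failed dose or an unstudied one. The probability of getting there runs from about 3% to 51% as the assumed DLT rate at 20 mg BID goes from 5% to 30%. The documents do not say where in that range the combination lies. The harm is confined to the MTD; patient safety and the recommended phase 2 dose are protected by other text. It should be fixed before the trial relies on these rules, because the branch is the one that level -1 exists for and the correction is small.

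**What to change.** **Section 6.3.** Add a row: if level 1 has two or more DLTs, 3 patients enter level -1, expanding to 6 if 0 or 1 of the 3 has a DLT, with no return to level 1.

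**Sections 7.2 and 8.4 and the Study Summary.** Reword the stop so that it bars the failing dose and all higher doses, while allowing level -1 and the expansion to 6 that 6.3 already requires. Replace both MTD definitions with one: no dose is named the MTD unless at least 6 patients were treated there and at most 1 of 6 had a DLT. If level -1 also has two or more DLTs, report that no MTD was determined.

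**Cost.** The wording change is one table row and three matching edits. Against the literal 8.4 stop, this branch needs 3 to 6 more formal-plan patients at level -1, so at most 6 + 6 = 12 in total, within the stated 24. That count is for level 1 failing before any escalation; if it fails only on later expansion, patients already treated at higher levels come on top. On other branches, up to 3 more patients are needed at the candidate MTD, including 50 mg BID after 0 of 3. Section 6.3 already asks for those patients at the recommended phase 2 dose.
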